14.2. Analysis Populations

The Intent-to-Treat (ITT) population will consist of all subjects consented in the study.

14.3. Statistical Analysis of Efficacy

Unless otherwise stated, all efficacy summaries and analyses will be conducted using the ITT population. All efficacy summaries and analyses will be produced for the following groups:

- Subjects treated in the study that were randomized to active treatment during the previous A101-WART 301/302 study.
- Subjects treated in the study that were randomized to vehicle during the previous A101-WART 301/302 study.
- Subjects treated in the study overall.
- Subjects not requiring treatment during the study that were randomized to active treatment during the previous A101-WART 301/302 study.
- Subjects not requiring treatment during the study that were randomized to vehicle during the previous A101-WART 301/302 study.
- Subjects not requiring treatment in the study overall.
- All subjects combined

The primary efficacy analysis will be the effectiveness of A-101 45% based on the proportion of subjects who achieve complete clearance (PWA=0) of all identified common warts at any scheduled visit. Any identified common wart for a subject that has missing PWA data will be treated as not clear for the purpose of the primary efficacy analysis.

Four secondary efficacy analyses will be performed:

- Durability of response: for warts achieving a status of Clear (PWA=0), the number of weeks the wart remains clear will be tabulated and these results will be summarized using descriptive statistics. The proportion of these warts that remain clear at the end of the study will also be presented.
- Mean per-subject percent of treated warts that are Clear (PWA=0) at each visit will be summarized using descriptive statistics.
- Proportion of subjects with a single wart at baseline whose wart is Clear (PWA=0) will be summarized using descriptive statistics by visit.
- Median time to achieve onset of Clearance (PWA=0) for all treated warts.

Efficacy summaries will be supported by listings of PWA data.

14.4. Statistical Analysis of Safety Data

Unless otherwise stated, all safety summaries will be conducted using the ITT population. All safety summaries will be produced for the following groups:

- Subjects treated in the study that were randomized to active treatment during the previous A101-WART 301/302 study.
- Subjects treated in the study that were randomized to vehicle during the previous A101-WART 301/302 study.
- Subjects treated in the study overall.
- Subjects not requiring treatment during the study that were randomized to active treatment during the previous A101-WART 301/302 study.
- Subjects not requiring treatment during the study that were randomized to vehicle during the previous A101-WART 301/302 study.
- Subjects receiving active treatment during the study or the previous A101-WART 301/302 study.

The proportion of subjects with treatment emergent adverse events will be tabulated and presented by System Organ Class and Preferred Term from the Medical Dictionary for Regulatory Activities (MedDRA). Likewise, the proportion of subjects with serious AEs will be summarized. Adverse event summaries will be presented showing the proportion of subjects experiencing adverse events, both overall and by MedDRA System Organ Class. The version of MedDRA to be used for the analysis of this study will be specified in the SAP.

Aclaris Therapeutics, Inc.

Protocol Number: A-101-WART-303

Protocol Version 3: 14 February 2019

Local skin reaction (LSR) scores and clinically relevant abnormal laboratory results will be tabulated and presented at the subject level. For each LSR sign and at each in-house visit, the proportion of subjects who had at least one treated wart with LSR severity ≥ 1 will be summarized.

Safety summaries will be supported by listings of all adverse events, laboratory results, and LSR data.

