#### 3.2 Treatment Groups and Data Presentation

This is an open-label study with only one treatment arm. Subjects who enter the study with a common wart receive study medication immediately. Subjects who enter the study with no common warts do not receive study medication at the start and will not be treated at all if they do not develop any common warts throughout the course of the study. In order to be eligible for this study, subjects must have completed protocol treatment on either the A-101-WART-301 or A-101-WART-302 study. Both WART-301 and WART-302 were double-blind studies where subjects were treated with either active A-101 45% topical solution or vehicle solution. To best account for all potential exposure to A-101 45%, summaries and analyses will take into consideration both the current open-label treatment status as well as the randomized treatment assignment from the subject's respective double-blind study. This classification precipitates the following four treatment groups.

- Open Label A-101 45%: Double-Blind A-101 45%
- Open Label A-101 45%: Double-Blind Vehicle
- Open Label Not Treated: Double-Blind A-101 45%
- Open Label Not Treated: Double-Blind Vehicle

Depending upon analysis population, data will be summarized into all or a subset of treatment groups indicated above. Summaries on All Enrolled Population will display all four treatment groups. Summaries on Safety Population will display only first two treatment groups.

All data listings will be sorted by treatment group and subject ID. Subject ID will identify site number and double-blind study subject participated prior to open label study

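### Safety columns label prior A-101 exposure by the parent-study arm assigned, not the solution received, so a subject given the wrong solution would carry the wrong exposure history

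*Protocol*

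**What the plan says.** Protocol 14.4 lists six groups for the safety summaries. Four are split by the arm assigned in the parent study. Two of these cover subjects treated in 303 ("Subjects treated in the study that were randomized to active treatment during the previous A101-WART 301/302 study" and "Subjects treated in the study that were randomized to vehicle during the previous A101-WART 301/302 study"), and two cover subjects who need no treatment in 303. Another group, "Subjects treated in the study overall", does not depend on the parent arm. The last is defined by receipt: "Subjects receiving active treatment during the study or the previous A101-WART 301/302 study".

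SAP 3.2 gives the purpose of its grouping as "To best account for all potential exposure to A-101 45" per cent. It then states that "summaries and analyses will take into consideration both the current open-label treatment status as well as the randomized treatment assignment" of the parent study. Crossing treated or not treated in 303 with double-blind A-101 or vehicle gives four groups. For the safety tables, "Summaries on Safety Population will display only first two treatment groups". Those are the two treated groups, and they differ only in randomized parent arm.

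The protocol's pooled treated group and its group defined by receipt are not among the SAP's four. SAP 3.14 explains the move from the ITT to the Safety Population and says that data from untreated subjects will be listed. It does not mention the as-received group. Neither document says how to classify a subject who was given the wrong solution in 301 or 302.

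**The concern.** The SAP's stated purpose is exposure, but the variable it uses is assignment. Randomized assignment is a sound basis for the efficacy summaries. A safety column meant to show who had A-101 before should rest on who received it.

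The label matters because the two safety columns separate subjects on a first A-101 course (prior vehicle) from those on a further course (prior A-101). Protocol 4.2 gives the need for multiple courses as the reason for the study, and Protocol 14.1 sizes it on subjects who have already received active treatment and are treated again. If a vehicle-arm subject was given A-101 in the parent study, that subject's 303 events would count as first-course events. For common events this hardly shows. For a rare or serious event, one case under the wrong history takes a column from none to some.

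**Working it through.** **1. Basis used for parent-study treatment**

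| Source | Groups | Basis |
|---|---|---|
| Protocol 14.4 | 4 of 6 | randomized parent arm |
| Protocol 14.4 | 1 of 6 (pooled treated) | parent arm not used |
| Protocol 14.4 | 1 of 6 (active in 303 or in the parent study) | receipt |
| SAP 3.2, Safety Population | 2 of 2 | randomized parent arm |

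For 303 itself the SAP does use receipt: SAP 3.1 requires at least one application for the Safety Population. Each safety column therefore combines receipt in 303 with assignment in the parent study.

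**2. Where prior exposure enters the safety tables**

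SAP 3.11.1 describes no exposure total that adds 301/302 to 303. The treatment cycles in SAP 3.3 and 3.11.3 count courses within 303 only. The column label is thus the only route by which parent-study exposure reaches the safety summaries.

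**3. The plan's own figure**

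Inputs from Protocol 14.1 and SAP 3.13: 400 recruited, 200 of them active in the parent study, 26% clear.
- Active-arm subjects needing A-101 again: 200 × (1 − 0.26) = 148. This reproduces the stated 148 and exceeds the target of 100.
- Vehicle-arm subjects enrolled: 400 − 200 = 200.

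**4. Subjects who would change label**

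The rule tested is: prior A-101 if any A-101 application was given in 301/302, otherwise prior vehicle. The documents give neither an error rate nor a vehicle clearance rate, so both are assumed: errors 0.5% to 2%, vehicle clearance 5% to 26%.
- Vehicle arm, enrolled: 200 × 0.005 = 1 to 200 × 0.02 = 4.
- Vehicle arm, treated in 303: 200 × (1 − 0.26) = 148 to 200 × (1 − 0.05) = 190. Relabelled: 148 × 0.005 = 0.74 to 190 × 0.02 = 3.8.
- Active arm: a subject moves only if no A-101 was ever given. If complete swaps occurred at the same rates, that is 148 × 0.005 = 0.74 to 148 × 0.02 = 2.96.
- Error rate of zero: nobody moves.

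**5. Effect on a difference between the two columns**

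Let pA and pV be the true event proportions with and without prior A-101, and m the share of a column that is mislabelled.
- Errors in the vehicle column only: the observed difference is pA − [(1 − m)pV + m·pA] = (1 − m)(pA − pV). The factor is 0.995 at 0.5% and 0.98 at 2%.
- Complete swaps at rate m in both columns: the factor is 1 − 2m, which is 0.99 at 0.5% and 0.96 at 2%.
- One misplaced event moves the vehicle column from 0 to between 1/190 = 0.5% and 1/148 = 0.7%.

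**The case against.** The strongest reply is that the problem is hypothetical. Neither document reports a dispensing error in 301 or 302, the rates above are assumptions, and SAP 3.8 and 3.11 refer to a separate data-handling specification that may contain a rule. All of this stands, and it limits the point to a low-priority improvement. It does not remove the mismatch between the purpose SAP 3.2 states and the variable it names.

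A second reply is that the protocol already has a pooled treated group and a group defined by receipt, and a subject treated in 303 is placed correctly in both. True, but every subject treated in 303 belongs to both whatever happened in the parent study, so neither separates a first course from a further one. Nor is either among the SAP's four groups.

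A third reply is that the repeat-exposure question has other evidence. SAP 3.11.3 summarizes local skin reactions by cycle, all adverse events are listed, and Protocol 13.1.5 leaves relatedness to the investigator. This also stands, so the label does not decide causality. But the cycles do not count the parent-study course, and SAP 3.2 sorts the listings by the same treatment groups.

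A reader might also infer that Protocol 14.4 contradicts itself because a vehicle-randomized subject can appear both in a vehicle group and in the any-active group. That is overlap by design: every vehicle-arm subject correctly dosed and then treated in 303 belongs in both.

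**Conclusion.** The point holds as a minor one. Both safety columns in the SAP, and four of the six protocol safety groups, record parent-study treatment as assigned, so a subject given the wrong solution would sit under the wrong prior-exposure history.

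On the assumed rates, 1 to 4 of about 200 enrolled vehicle-arm subjects would change label. Among those treated in 303 it is about 0.7 to 3.8, plus any active-arm subject who never received A-101. A difference between columns would shrink by at most about 4%, even with complete swaps in both arms at 2%. The summaries are descriptive, and no sample-size figure depends on the label.

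Three stronger readings are not supported:
- **303 events credited to the wrong product.** SAP 3.14 says that all treated subjects use the same medication, A-101 45%, so only the historical label can be wrong.
- **A cumulative exposure total misplaced.** The SAP describes no such total.
- **An error rate applied to all 400 enrolled (0.5% to 2% of 400 = 2 to 8 subjects).** This counts active-arm subjects who received some A-101 and would not move, and subjects untreated in 303, whom the safety tables do not show.

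**What to change.** - In SAP 3.2, for the safety, exposure and local-skin-reaction summaries, define the prior-treatment factor as the double-blind solution actually received: prior A-101 if any A-101 application was given in 301/302, otherwise prior vehicle. This also settles subjects who received both solutions.
- Keep randomized assignment for the efficacy summaries.
- In Protocol 14.4, bring the four groups split by randomization into line with this rule. The pooled treated group and the as-received group need no change.
- Restore the as-received group in the SAP, or explain in SAP 3.14 why it is omitted. Everyone treated in 303 has received A-101, so beyond the Safety Population this group adds only subjects who had A-101 in the parent study and no treatment in 303. Restoring it means tabulating their safety data as well as listing it.

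The cost is a few lines of SAP wording, matching protocol wording, and one actual-treatment variable from the parent-study datasets. Setting the rule in advance avoids deciding where a subject belongs after the event is known.

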9. STUDY ASSESSMENTS

9.1. Identification of Common Warts

Subjects who have completed participation in the A-101-WART 301 or A-101-WART-302 study are eligible to enroll into the A-101-WART -303 study. Subjects that were previously treated on the double-blind phase 3 study whose warts have recurred, were not treated or who develop new warts during the observation period of A-101-WART -303 are also eligible to receive treatment with A-101 Topical Solution 45% twice a week for 8 weeks. An 8-week treatment period may begin anytime between Day 1 and Day 122.

Warts that are identified by the treating investigator must meet the following criteria:

- Subject may have 1 wart and up to 6 common warts treated during an 8-week treatment period
- Identified warts must have a longest axis of ≤ 8 mm.
- Be a discrete lesion, i.e. each wart meeting the entry criteria must be clearly separated from other warts
- Not be a periungual, subungual, genital, anal, mosaic, plantar, flat or filiform wart
- Not be in an intertriginous fold
- Not be covered with hair which, in the Investigator's opinion, would interfere with the study medication treatments or the study evaluations

Not be in an area that may be occluded (e.g., by clothing or footwear or in a skin fold).

Each identified wart will be identified on the body charts in the subject's eCRF.

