10.5. Study Medication Treatment

The study medications are for external, topical use only and are to be applied only to those subjects that have been properly consented and randomized to the study.

The investigational center staff member must comply with the study medication storage conditions outlined in Section 10.1.

Subjects who have warts identified for treatment with A-101 Topical Solution, 45% will be instructed to treat each wart according to the technique outlined in Section 10.7. Subjects that are 18 years of age and older will apply their own study medication and subjects age 1 to 17 will have their study medication applied by a parent or legal guardian.

Identified warts are to be treated twice a week for up to 8 weeks (maximum 16 applications) or until the wart has cleared. Subjects are to be instructed to apply the A-101 study medication on the following days: Day 1, Day 4, Day 8, Day 11, Day 15, Day 18, Day 22, Day 25, Day 29, Day 32, Day 36, Day 39, Day 43, Day 46, Day 50 and Day 53. A window of +1 day is allowed.

Subjects (or parents/legal guardians) are to apply the A-101 study medication in the office on the following days: Day 1 and Day 29.

[figure not shown]

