**Table 3 Safety Observation Assessments for Subjects that are Clear at Visit 1 and Remain Clear**

Visit	V1	V2	V3	V4	V5
Treatment Day	Day 1	Week 6 (Day 42)	Week 12 (Day 84)	Week 18 (Day 126)	Week 26 (Day 182)
Window		+7 Days	+7 Days	+7 Days	+2 Days
In Office Visit	▲ 				▲
Phone Call		▲ 	▲ 	▲ 	
Informed Consent	▲				
Inclusion Criteria/Exclusion Criteria	▲				
Concomitant therapies		▲	▲	▲	▲
Adverse Events	▲	▲	▲	▲	▲

Visit 1 of A-101-WART 303 may occur on the same day as Visit 13 of A-101-WART 301 or A-101-WART 302.

 Investigational site staff will contact via a documented phone call on Visit 2 Day 42, Visit 3 Day 84, Visit 4 Day 126 and Visit 5 Day 182. During the phone calls sites are to ask the subject if they have had any new warts develop or if a wart that was previously treated has recurred. If a subject has had a new wart develop or a previously treated wart has recurred, then the subject is to be scheduled for an in -office visit to start an 8-week treatment course with A-101 study medication. Subjects are to be instructed to contact the investigational site as soon as they think a new wart (or a recurrence) has developed. The 8-week treatment period can start no later than Day 102. Refer to [Table 2](#) for the 8- week treatment schedule.

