### 3.3 Study Day and Period Study Day

As shown in [Figure 1](#), subjects can potentially take multiple courses of treatment throughout the study. Subjects entering the study with warts will receive treatment at study entry as shown in [Table 2](#). Subjects who enter without any common warts do not receive study medication immediately and follow visit schedules shown in [Table 3](#). If these subjects develop any wart during the study, they will then begin a treatment regimen and follow the visit schedule for treated subjects. Subjects can initiate a treatment regimen up to three times (cycles) throughout the course of the study up to day 122. To allow for comparisons referencing each treatment cycle, Study Day will be calculated in two ways. Study day is defined as the relative day in the study from time of enrollment (first dose if treated immediately). Period study day is defined as the relative day from the day of first dose within a treatment cycle.

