### **3.11.2 Adverse Events**

Adverse events are coded using the MedDRA (Version 22) and are categorized by system organ class (SOC) and preferred term (PT). Only treatment emergent adverse events are included in summary tabulations (i.e. adverse events occurring within 30 days of each application of study medication). All adverse events are included in the data listings including those that are not considered treatment emergent.

To allow differentiation as to which study period an Adverse Event occurred, three categories are defined based upon onset date. Adverse Events that had onset dates prior to the first application of study medication are considered "prior". Adverse events with onset dates on or within 30 days of an application of study medication are considered "treatment emergent". Events with onset dates more than 30 days after the most recent application of study medication are considered as "post-therapy." In this study, subjects can possibly receive medication up to three cycles and multiple doses of medication within a treatment cycle. The above rule will be applied to all known doses of medication while determining study period.

Frequency tabulations are presented by MedDRA SOC and preferred term, for all adverse events; study treatment-related adverse events, adverse events resulting in discontinuation of study treatment, serious adverse events and adverse events by maximum severity. Adverse events resulting in discontinuation are those with 'action taken' recorded as 'drug withdrawn'.

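### Treatment-emergent adverse events are planned only as crude subject proportions, although countable time under the SAP's 30-day rule runs from about 61 to 182 days

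*Protocol*

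**What the plan says.** **Measure.** Protocol 14.4: "The proportion of subjects with treatment emergent adverse events will be tabulated and presented by System Organ Class and Preferred Term". SAP 3.11.2: "Frequency tabulations are presented by MedDRA SOC and preferred term, for all adverse events; study treatment-related adverse events", and likewise for discontinuations, serious events and maximum severity. Neither document plans a person-time denominator, a time-to-first-event summary or an AE table by treatment cycle.

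**Which events count.** Only treatment-emergent events enter the tables. SAP 3.11.2: "Adverse events with onset dates on or within 30 days of an application of study medication are considered" treatment emergent, with the rule applied to every known dose. Protocol 14.4 itself defines no window.

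**How much treatment a subject can have.** SAP 3.3: "Subjects can initiate a treatment regimen up to three times (cycles) throughout the course of the study up to day 122". Protocol 9.1: "An 8-week treatment period may begin anytime between Day 1 and Day 122". The SAP's Table 3 footnote differs: "The 8-week treatment period can start no later than Day 102". Protocol 10.5 lists 16 application days per course, ending "Day 46, Day 50 and Day 53. A window of +1 day is allowed". Under Protocol 13.1.3, AE collection runs to the last study visit.

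**Columns.** SAP 3.2: "To best account for all potential exposure to A-101 45%, summaries and analyses will take into consideration both" current open-label status and prior randomized treatment. Safety Population tables show two columns: treated subjects previously on A-101, and treated subjects previously on vehicle.

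**Related summaries.** SAP 3.11.1 describes duration of treatment and number of applications but does not link them to AEs. SAP 3.11.3 gives a by-cycle summary for local skin reactions (LSRs) only.

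**The concern.** Each subject's time at risk of a countable event depends on how many courses were taken, when they began and when the subject left. These follow wart response, new or recurrent warts and the latest permitted start day, and they need not be alike in the two prior-treatment columns. Subjects still with warts at entry start on Day 1 and may repeat; subjects clear at entry start late or never. A crude proportion gives a subject observed for 61 countable days the same weight as one observed for 182.

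What is at stake is how the safety tables can be read. A difference between columns could reflect countable time rather than event rate, and a real difference could be hidden by shorter windows in one column. The exposure summaries would let a reader suspect this but not resolve it.

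**Working it through.** **The plan's own figures.** The documents give no window length and no AE rate. The one computed figure nearby is the 148 prior-active subjects expected to need treatment (Protocol 14.1): 400 × 0.5 × (1 − 0.26) = 148. It reproduces but is not an input here.

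**Step 1: countable days.** Inputs: applications on course Days 1 to 53 (Protocol 10.5), a 30-day window after each (SAP 3.11.2), end at Day 182. A course starting on Day s is countable from Day s to Day s + 52 + 30, cut at Day 182. Gaps between applications are at most 4 days, so the window is unbroken. Repeat courses are taken to start on Day 60 (Visit 5) and 59 days later, on Day 119.

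| Completed courses | Countable period | Days |
|---|---|---|
| One, from Day 122 | 122 to 182 | 61 |
| One, from Day 102 | 102 to 182 | 81 |
| One, from Day 1 | 1 to 83 | 83 |
| Two, from Days 1 and 60 | 1 to 142 | 142 |
| Three, from Days 1, 60 and 119 | 1 to 182 | 182 |

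The ratio of extremes is 182/61 = 3.0. Using the +2-day window of the final visit, the extremes are 63 and 184. A subject who stops after one application has 31 days, so the spread including early stoppers is wider.

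**Step 2: effect on one subject's probability of an event.** The rate is assumed constant, with a 20% risk in 83 days: λ = −ln(0.8)/83 per day, and P(t) = 1 − exp(−λt). For 61, 83, 142 and 182 days this gives 15.1%, 20.0%, 31.7% and 38.7%. With a 10% risk in 83 days it gives 7.5%, 10.0%, 16.5% and 20.6%.

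**Step 3: effect on a column.** A column averages P(t) over its course mix. The mixes below (one/two/three courses, all from Day 1) are assumptions, at a 20% risk in 83 days.

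| Mix, column 1 | Mix, column 2 | Crude %, same rate |
|---|---|---|
| equal | equal | no gap |
| 55/25/20 | 45/30/25 | 26.7 v 28.2 |
| 70/20/10 | 30/30/40 | 24.2 v 31.0 |

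For example, 0.70 × 20.0 + 0.20 × 31.7 + 0.10 × 38.7 = 24.2. At a 10% risk the last row becomes 12.4 v 16.2. Adding late starters, with assumed mixes of 61/83/142/182-day windows of 15/45/25/15% v 5/20/30/45%, gives 6.5 v 8.5 at a 5% risk and 36.5 v 45.3 at a 30% risk.

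**Step 4: would a rate settle it?** Suppose instead that every subject has a 20% risk, all of it spread evenly over the first 31 days (mean about 15.5 days). Crude proportions are then 20% whatever the course count. The rate per 100 person-years, with time stopped at first event, is 0.2 / (0.8 × T + 0.2 × 15.5) × 36,525:

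- T = 83: 0.2/69.5 × 36,525 = 105
- T = 142: 0.2/116.7 × 36,525 = 63
- T = 182: 0.2/148.7 × 36,525 = 49

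For the mixes 70/20/10 and 30/30/40, mean T is 104.7 and 140.3 days, and the rates are 84 and 63. The column with more courses looks safer at identical risk.

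**The case against.** The plan describes a single-arm, open-label study. It promises no between-column AE comparison, test or decision rule, and SAP 3.14 stresses that all treated subjects receive the same medication. Protocol 14.4 also lists pooled groups. Exposure is described in SAP 3.11.1, all AEs are listed, and the direct look at repeated courses is the by-cycle LSR summary. The threefold spread is between subjects, whereas columns average over subjects. No course mix is documented, so any column-level gap is assumed. The 61-day figure depends on which latest start day holds. Finally, LSRs and other reactions during the 20-minute observation after in-office applications must be recorded as AEs (Protocol 12.1), so early clustering is plausible and rates could mislead.

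Most of this stands, and it limits the point. A reader might infer that prior A-101 versus prior vehicle is the plan's main test of cumulative exposure. SAP 3.2 says only that summaries take prior assignment into account. A reader might also infer that the tables will be distorted by some 7 percentage points, or that rates should replace proportions. The first rests on one assumed pair of mixes, and Step 4 shows why the second fails.

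What does not stand is that existing summaries close the gap. Side-by-side columns are read side by side without a test, and nothing planned relates AEs to countable time or to course number.

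**Conclusion.** The point holds as a limit on interpreting the primary objective, not as a calculation error. For completed courses, countable time ranges from 61 to 182 days, or from 81 days if the Day 102 limit governs late first starts. The SAP text on Day 102 and Day 122 must be reconciled; the 182-day figure assumes that the three courses and Day 122 of SAP 3.3 apply.

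Crude percentages in the two columns can therefore differ at the same event rate. How much, and in which direction, cannot be known from the documents. Under an assumed constant rate and a 20% risk in 83 days, the gap runs from zero with equal mixes, through 1.5 points (26.7% v 28.2%), to 6.8 points (24.2% v 31.0%). Neither crude proportions nor rates are sufficient alone: the former ignore countable time, and the latter depend on a roughly constant hazard. The addition is a cheap improvement worth making.

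**What to change.** In SAP 3.11.2:

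- Keep all crude counts and percentages.
- Beside them, add exposure-adjusted incidence for any treatment-emergent AE, related events, SAEs and the common preferred terms. This is subjects with the event divided by subject-time inside the SAP's own 30-day windows, with time stopped at first event, withdrawal or last visit.
- Show median countable time in each column header.
- Add a by-cycle AE table parallel to the LSR summary in SAP 3.11.3. Windows of successive courses overlap (a second course from Day 60 begins before Day 83), so state a rule for assigning events, such as to the course most recently begun. Show countable time per cycle too: under that rule a first course followed by a second on Day 60 has 59 days (Days 1 to 59), against 83 if none follows.
- State that crude, rate and by-cycle results will be interpreted together, and that no between-column statement will rest on the rates alone.

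Separately, reconcile the latest course start day between SAP Table 3, SAP 3.3 and the protocol.

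The cost is a few extra derivations and tables. The dates needed are those already used to classify events as treatment emergent; design, treatment and data collection do not change.
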